### Statistical Analysis Plan

**Descriptive analyses of *Rose* use.** We will compute the total number and percent of times sessions of each different duration were listened to (i.e., 5, 10, or 20 minutes) and the number of percent that each different voice were listened to across the entire study period for both groups.

**Feasibility analyses.** To evaluate the feasibility of *Rose*, and for both studies, we will first compute the mean, standard deviation, median and range for the number of times participants in the Access conditions listened to sessions as well as the number and percent of the participants who listened to a session at least four times during the first four weeks of access (i.e., per protocol). To evaluate satisfaction with use of *Rose*, we will compute the average satisfaction rating for those participants in the Access groups who listened to at least one session during the first four weeks of access, as well as the number and percent of the responses to each of the satisfaction response options. To evaluate interest in continued access to *Rose*, we will compute the average of the interest ratings of the participants in the Access groups who used *Rose* per protocol (i.e., at least four times during from baseline to the 4-week assessment point), as well as the number and percent of the responses to each of the interest question response options. To understand the participants' willingness to pay for continued access to *Rose*, we will compute the number and percent of responses to each of the payment question response options for the Access group participants in each study who had used *Rose* per protocol. Given the inherent differences between the two studies, Fisher's exact tests will be used to compare satisfaction and interest for continued access between the two studies. To assess the usability of *Rose*, we will compute the average SUS for participants in the Access groups of each study who had used at least once.

**Clinical effects analyses.** In order to estimate the possible effects of *Rose* on clinical outcomes, we will conduct two types of analyses. First, to estimate the immediate effects of the *Rose* sessions that target pain intensity, we will compute the ranges and average pre- to post-session changes in current pain intensity ratings for each participant individually (including participants in the Access condition who had access to 8 full weeks from baseline to the 8-week assessment point, and participants in the waitlist condition who had access for 4 weeks from the end of week 4 to the end of week 8 assessment point) and compute the median, minimum, and maximum of these values. Median statistics will be computed as the measure of central tendency given that the distributions of these changes were anticipated to be positively skewed (i.e., we anticipate that most participants would access *Rose* about four times during every 4-week period of access, but a fewer number might access *Rose* many times). Of interest is the general consistency of responses to the *Rose* sessions both within and between individuals. We will also conduct a linear mixed-effects model for the pre- to post-session change in pain intensity, including a random intercept for each participant to account for clustering (one for each study), to estimate the effect size and

significance levels of these changes. Given the possibility that participants who found *Rose* to be particularly effective may choose to listen to more sessions than those who found *Rose* to be less effective, as a sensitivity analysis, we will assess if there is evidence of informed cluster sizes by testing if the effectiveness of *Rose* is associated with the number of times sessions were listened to. This allows us to determine if the magnitude of the pre- to post-session improvements in pain intensity and mood are associated with frequency of listening (i.e., if those who reported more benefits tended to listen more often, which could bias the estimates of average benefit).

Next, we will calculate the mean and standard deviation for each of the five continuous outcomes and baseline, 4-weeks, and 8-weeks stratified by treatment condition (Access vs. Waitlist group). Standardized effects will be calculated to determine the within group change between baseline and both 4- and 8-weeks as well as the between group difference in these changes. As this is feasibility study, no rigorous test of significance will be performed. However, 95% confidence intervals will be computed for the between group effect sizes to determine the range plausible effect sizes in the population.

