## **Study Protocol and Statistical Analysis Plan**

**Title: Digital Clinical Hypnosis for Chronic Pain Management**

**NCT number: NCT06050083**

**Document date: 08/21/2025**

## Study Protocol

### Overview of Study 1 and Study 2

This protocol describes two studies that are a part of this project. They use the same experimental design to evaluate the feasibility of the digital program. The primary difference is that first study (Study 1) recruits individuals with chronic low back pain and the second (Study 2) recruits individuals with general chronic pain (which includes individuals with chronic low back pain as well as individuals with chronic pain as a secondary condition to another health problem, such as spinal cord injury). Both studies aim to enroll 50 participants, which, given an estimated 20% dropout rate, would allow for complete data from at least 40 participants in each study.

Both studies use a 2-arm prospective randomized controlled trial design to evaluate the feasibility of the program (called *Rose*) over an 8-week period. Participants are randomly assigned to one of two groups: *Rose* access for a full 8 weeks (Access group) or *Rose* access for 4 weeks (Waitlist control group). The Waitlist group will not have access to *Rose* for the first 4 weeks of the study and then have access to *Rose* for the final 4 weeks. The 4-week assessment point is the primary study endpoint. Primary (feasibility) and secondary (clinical) outcomes using the *Rose* program and self-report measures using the Research Electronic Data Capture (REDCap) program, hosted by the University of Washington Institute of Translational Health Sciences (ITHS). Participants complete the self-report measures at three timepoints: baseline (before randomization), 4 weeks after randomization (primary endpoint), and 8 weeks after randomization.

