### Measures

**Feasibility.** The studies has five primary feasibility outcome domains: (1) frequency of listening to a hypnosis session; (2) participant satisfaction with *Rose*; (3) interest in having continued access to *Rose* after study completion; (4) willingness to pay for that continued access; and (5) system usability. For each feasibility outcome, we have *a priori* specific criteria for determining if *Rose* was feasible.

**Frequency of access.** The *Rose* application tracks how frequently participants listened to a session. In this domain, we propose that *Rose* would be feasible if at least 50% of the Access participants who were offered access to *Rose* used it at least once/week. This criterion was selected as clinical hypnosis sessions are usually scheduled to occur once/week, making this frequency a standard for this treatment.

**Satisfaction with *Rose*.** We assess satisfaction with *Rose* at the 4-week timepoint (i.e. 4-weeks after randomization) using a 5-point global treatment satisfaction scale ("Taking all things into account, how satisfied are you with using the *Rose* web application?"), whose response options ranged from 1 ("Very satisfied") to 5 ("Very dissatisfied"), or "Prefer not to Answer." We determined that *Rose* would be feasible if  $\geq$  50% of the participants who listened to at least one *Rose* session would rate being either "Somewhat satisfied" or "Very satisfied" with *Rose*.

**Interest in continued *Rose* access.** We assess interest in continued access to *Rose* by asking, that if the program were available, "... how interested would you be in downloading and using this application?" Participants respond to this question using a 5-point Likert scale ranging from 0 = "I would not be interested" to 5 = "I would be extremely interested." We determined that *Rose* would be feasible if  $\geq$  50% of the

Access group participants who used *Rose* per protocol (i.e., at least 4 times during the four weeks after randomization) rated themselves as being at least "... a little interested" in using *Rose*.

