**Willingness to pay for access to *Rose*.** We also assess participants' willingness to pay for continued *Rose* access after finishing the study. However, after the study began, we discovered that the question had been phrased incorrectly. The error was corrected when the error was discovered, but most of the Study 1 participants and four of the Study 2 had responded to the incorrectly worded question when the question was corrected. We therefore present the findings for this question only for the Study 2 participants in the Study 2 participants in the Access group who used *Rose* per protocol. We determined *a priori* that *Rose* would be feasible if  $\geq 40\%$  of the Access group participants who used *Rose* per protocol endorsed a willingness to pay for continued access.

**Usability.** Finally, we assess the usability of *Rose* using the System Usability Scale (SUS)(Lewis, 2018), a common 10-item measure of the overall usability of applications (sample item, "I thought the product was easy to use"). The cutoff we selected as the minimum average needed to determine that *Rose* was feasible was a score of  $\geq 68$ , which is the average SUS score across a large variety of software products (i.e., if *Rose*'s SUS score is  $\geq 68$ , it has an above average level of usability; (Banger, Kortum, & Miller, 2008)).

**Secondary outcomes: Changes in clinical domains.** Study 1 and Study 2 were both feasibility studies and are therefore not powered to detect statistically significant effects on any clinical outcome. However, the primary purpose of *Rose* is to improve pain-related quality of life domains for individuals who access and listen to *Rose*'s sessions, and these two feasibility studies were designed to provide data which could be used to inform a full clinical trial, if *Rose* is found to be feasible. A secondary aim of the two feasibility studies was therefore to provide preliminary estimates of the effects of *Rose* on a number of pain-related clinical outcomes to: (1) determine if anticipated improvements in these outcomes could be observed and, if so, to help (2) identify (a) the outcome domains that should be assessed in a fully-powered clinical trial, and (b) the measures that should be used to assess those domains in such a clinical trial.

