We assess six clinical outcome domains: (1) immediate (i.e., pre- to post-session) changes in pain intensity; (2) change in average pain intensity from baseline (i.e., at randomization) to four weeks after randomization (primary endpoint) and to eight weeks after randomization (secondary endpoint); (3) change in pain interference from baseline to 4-weeks and from baseline to 8-weeks; (4) change in anxiety from baseline to 4-weeks and baseline to 8-weeks; (5) change in sleep disturbance from baseline to 4-weeks and baseline to 8-weeks; and (6) change in opioid use from baseline to 4-weeks and baseline to 8-weeks after randomization.

We measure pain intensity for the first two clinical outcomes using a 0-10 Numerical Rating Scales (NRS) of pain intensity. The endpoints of the NRSs used here were 0 = "No pain" and 10 = "Pain as bad as you can imagine." NRSs have a great deal of evidence supporting their reliability and validity as measures of pain intensity (Jensen, 2018) and are recommended over other ratings scale in pain clinical trials (Dworkin et al., 2005). To assess immediate changes in pain intensity associated with

listening to a *Rose* session, the *Rose* application prompts participants with a screen/question asking participants to rate their *current pain* on the 0-10 NRS just before and just after each listening session that included hypnotic suggestions for comfort. To assess change in average pain intensity from baseline to the 4-week and the 8-week assessment points, participants are asked to rate their "Average pain intensity in the past week" with the NRS at baseline (immediately after randomization), and then 4- and 8-weeks after randomization.

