Pain interference, anxiety, and sleep disturbance at baseline, week 4, and week 8 are assessed by administering the Patient Reported Outcomes Measurement Information System (PROMIS) 8-item short form scales assessing these domains (PROMIS, 2024). PROMIS measures ask respondents to consider the magnitude or frequency of each symptom in the past seven days listed on the short forms using 5-point Likert scales with the response options responses varying as a function of the item (e.g., for magnitude, "Not at all" to "Very much"; for frequency, "Never" to "Always"). Responses are summed and then transformed to T-scores with a mean of 50 and a SD of 10 in the normative samples. All PROMIS measures are scored such that higher scores indicate higher levels of the domain being assessed (i.e., here, more pain interference, anxiety, or sleep disturbance). Evidence supports the validity and reliability of each of these measures in a variety of clinical populations, including individuals with chronic pain (Bhandari et al., 2022; Chimenti et al., 2021). The baseline internal consistencies (Cronbach's alphas) for these measures were: .95, .95, and .90 for Study 1 and .93, .86, .91 for Study 2 the PROMIS Pain Interference (8-item Short Form), PROMIS Anxiety (8-item Short Form), and PROMIS Sleep Disturbance (8-item Short Form) scales, respectively.

Opioid use is assessed by a self-report question asking participants if they are taking any opioid medications (with opioid examples listed, such as oxycodone, hydrocodone, and fentanyl). If the participant responded "Yes," a sub-question appeared asking for: medication name, dosage, and frequency of use in the past seven days. These participant responses were then converted to Morphine Milligram Equivalents (MME), which refers to "the amount of morphine that an opioid dose is equal to when [the opioid is] prescribed." MME converts different opioid medication dosages into a single unit and is calculated by comparing the results from two publicly available MME calculators (Hudson et al., 2018).

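### Does a four-session total fail to answer a criterion worded as use once a week?

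*Combined protocol and SAP*

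**What the plan says.** Measures (Frequency of access) calls the program feasible if at least 50% of the Access participants offered it "used it at least once/week. This criterion was selected as clinical hypnosis sessions are usually scheduled to occur once/week". It gives no window and does not say whether the rate is an average or must hold in every week. The data source is that the "application tracks how frequently participants listened to a session".

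The Statistical Analysis Plan (Feasibility analyses) summarises session counts in the Access groups by mean, standard deviation, median and range, and adds a count of participants together with the "percent of the participants who listened to a session at least four times during the first four weeks of access (i.e., per protocol". Its other use percentages are shares of sessions by duration and by voice, not shares of participants.

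Two further places bear on the reading. Measures (Interest in continued access) defines per-protocol use as "at least 4 times during the four weeks after randomization". The Overview states: "The 4-week assessment point is the primary study endpoint".

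**The concern.** The criterion is worded as a weekly frequency and justified by the weekly scheduling of clinical hypnosis, which suggests regularity. The planned percentage is a total. A participant who listens four times in week 1 and never again is counted as meeting it. No sentence says that four sessions in four weeks is what the weekly criterion means, and a mean, median or range of totals cannot recover timing.

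This is a pass/fail primary outcome. If the two readings gave opposite verdicts, a pass on the total could be reported as if half the group had listened every week. The SAP (Clinical effects analyses) also expects most participants to listen about four times per four-week period. At exactly four sessions, every week is covered only when there is one session in each.

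**Working it through.** **Stated design figure.** The Overview's enrolment reproduces: 40/(1 − 0.20) = 50 per study. It does not bear on the point except as the source of the group size assumed below.

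**The average reading.** Four sessions over four weeks is 4/4 = 1.0 per week. On that reading the SAP percentage is the criterion, over the window that ends at the primary endpoint.

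**The bound.** At least one session in each of four weeks gives a total of at least 4. The converse fails: weekly counts of (0, 0, 0, 4) reach the total with three empty weeks. For exactly four sessions at random times, the chance of covering all four weeks is 4!/4⁴ = 24/256 = 9.4%.

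**Size of the gap.** The documents give no data on session timing, so every model here is an assumption. For constant Poisson use at rate L per week, let p = 1 − exp(−L). Then:

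- total of at least 4: P(N ≥ 4) with N Poisson, mean 4L
- active in all four weeks: p⁴
- active in at least three weeks: p⁴ + 4p³(1 − p)

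At L = 1, p = 0.632, which gives 56.7%, 16.0% and 53.1%. The gamma rows let users differ in rate (shape 1). The halving row has mean weekly use of 3.2, 1.6, 0.8 and 0.4, which sums to 6. The seven-day rows use a uniform start day with normal scatter around weekly spacing, from 1,000,000 simulated users.

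| Assumed use | ≥4 sessions, % | All 4 weeks, % | ≥3 of 4 weeks, % |
|---|---|---|---|
| Poisson 0.75/week | 35.3 | 7.8 | 35.5 |
| Poisson 1/week | 56.7 | 16.0 | 53.1 |
| Poisson 1.5/week | 84.9 | 36.4 | 78.3 |
| Poisson 2/week | 95.8 | 55.9 | 90.9 |
| Gamma, mean 1/week | 41.0 | 20.0 | 40.0 |
| Gamma, mean 1.5/week | 54.0 | 31.6 | 52.6 |
| Gamma, mean 3/week | 72.6 | 53.4 | 71.2 |
| Halving each week, mean 6 in total | 84.9 | 13.9 | 57.6 |
| Every 7 days, no scatter | 100 | 100 | 100 |
| Every 7 days, SD 1 day | 92.0 | 72.0 | 95.7 |
| Every 7 days, SD 2 days | 84.1 | 45.2 | 91.0 |

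Under Poisson use, the total and the all-weeks share fall on opposite sides of 50% only between about 0.92 and 1.84 sessions per week. Under the gamma mixture they do so only between means of about 1.32 and 2.69. In every row, the total and the at-least-three-weeks share fall on the same side of 50%.

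**In a group of 25.** No allocation ratio is stated. Assuming 50 split 1:1, half of 25 is 12.5, so a pass needs 13. The chance that the total passes and the all-weeks count does not is 6.4% at Poisson 0.75/week, 75.0% at 1, 91.9% at 1.5, 27.5% at 2 and 1.3% at 2.5. For seven-day use with a one-day scatter it is 0.95%.

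**The case for a change.** The best case for a change is that a prespecified pass/fail rule has two readings, the plan does not choose between them in words, and the anticipated use of about one session a week lies inside the Poisson range where verdicts differ. Data collection had also begun when the document was dated: it reports that "most of the Study 1 participants and four of the Study 2 had responded to the incorrectly worded question", and it gives observed baseline reliabilities. A rule left undefined at that stage could be settled after the results are seen. The remedy would be cheap: one sentence and a small table of active weeks.

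The logical bound stands, and so does the missing linking sentence. The rest is weaker.

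- **Room for choice.** The SAP computes one percentage of participants by use. An analyst who follows it has no second figure to switch to.
- **Closeness to the cutoff.** The expectation of about four sessions concerns individual counts and was written to justify medians. It does not place the group share near 50%.
- **The large gaps.** They come from random session times or steep early decline, judged against an all-four-weeks standard in fixed bins that the documents never set. Those bins also misclassify near-weekly users: sessions on days 1, 7, 15 and 22 leave week 2 empty.
- **The extra table.** Pain ratings are prompted "just before and just after each listening session that included hypnotic suggestions for comfort", which suggests session-level records, but nothing says that they are dated. The table might not be possible, and it would be a descriptive addition rather than a better test.

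**Conclusion.** No change to the plan is needed. The criterion does not define its window or its averaging, but the SAP supplies a definition that equals once a week on average, matches the per-protocol definition in Measures and ends at the primary endpoint. Analysts would fill the gap this way without difficulty, and followed as written the plan gives a sound answer on the reading its own text supports.

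A pass shows average use of at least one session a week over four weeks in at least half of the Access group. It does not show use in each week, and no section plans to claim that.

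The chance of a verdict opposite to an every-week count, about 1% to 92% across the cases given for 25 participants, rests on assumed timing and an assumed 1:1 split, and the documents cannot narrow it. The conclusion would differ only if the sponsor meant a session in every calendar week, which nothing in the text states.

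### Measures and the SAP give different analysis sets for willingness to pay, and neither says whether the four misworded Study 2 answers count towards the 40% criterion

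*Combined protocol and SAP*

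**What the plan says.** The Measures section (Willingness to pay) discloses that the payment question was phrased incorrectly and corrected after the study began, by which time "most of the Study 1 participants and four of the Study 2 had responded to the incorrectly worded question when the question was corrected". It draws a consequence: "We therefore present the findings for this question only for the Study 2 participants in the Study 2 participants in the Access group", with per-protocol use of Rose as a further condition. The next sentence sets the criterion at 40% or more "of the Access group participants who used *Rose* per protocol endorsed a willingness to pay for continued access", with no limit to Study 2 or to people who saw the corrected question.

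The Statistical Analysis Plan (Feasibility analyses) plans the number and percent of the "payment question response options for the Access group participants in each study who had used" Rose per protocol. It mentions neither the wording error nor the restriction to Study 2 nor any exclusion. It attaches no threshold to this table, and payment is not part of the cross-study comparison: "exact tests will be used to compare satisfaction and interest for continued access between the two studies".

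**The concern.** There are two separate problems.

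**Study 1.** One section withholds the Study 1 payment result because most of the answers are to the wrong question. The other plans to compute it. Both are current text, and they cannot both be followed as written. Since the SAP neither tests payment nor sets a threshold for it, this is a conflicting descriptive table, not a conflicting test.

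**Study 2.** The remedy in Measures is to drop Study 1, not to drop misworded answers. Read literally, its set (Study 2, Access, per protocol) still admits any of the four who meet that description. The sentence that defines the set repeats a phrase, so its intended wording is unclear.

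At stake is the pass or fail result on a primary feasibility domain, in a set small enough for a few answers to matter. With no written rule, the choice to keep or remove the four can be made after their answers are known.

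**Working it through.** **Inputs from the documents**

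- Enrolment (Overview): "Both studies aim to enroll 50 participants", with an estimated 20% dropout and at least 40 with complete data. This reproduces: 40 / (1 − 0.20) = 50.
- Criterion (Measures): at least 40% of per-protocol Access participants.
- Misworded answers in Study 2 (Measures): four, with arm and per-protocol status not stated.
- Use criterion (Measures, Frequency of access): "at least 50% of the Access participants who were offered access to" Rose using it at least once a week.

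**Assumptions**

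The allocation ratio and the per-protocol count are not stated. I assume 1:1 allocation and take three sizes *n* for the Study 2 per-protocol Access set:

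- *n* = 25: 50/2, with no losses.
- *n* = 20: 25 × 0.80, with every completer per protocol.
- *n* = 13: the use criterion just met, 25 × 0.50 = 12.5, rounded up.

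**Method**

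Let *k* (0 to 4) be the number of misworded answers in the set, *m* = *n* − *k* the valid answers, *y* the valid yes answers, and *j* (0 to *k*) the misworded yes answers. The verdict depends on the handling rule when *y*/*m* ≥ 0.40 and (*y* + *j*)/*n* ≥ 0.40 disagree. The table lists every valid result for which some *j* produces a disagreement.

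| *k* | *n* = 13 | *n* = 20 | *n* = 25 |
|---|---|---|---|
| 0 | none | none | none |
| 1 | 5/12 | 7/19 | 9/24 |
| 2 | 4–5/11 | 6–7/18 | 8–9/23 |
| 3 | 3–5/10 | 5–7/17 | 7–9/22 |
| 4 | 2–5/9 (22% to 56%) | 4–7/16 (25% to 44%) | 6–9/21 (29% to 43%) |

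At each *n*, exactly *k* values of *y* can flip. Outside these windows the verdict is the same under either rule.

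**Worked cases at *n* = 20, *k* = 4**

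The pass mark is 8/20 with the four kept, since 0.40 × 20 = 8. It is 7/16 with them removed, since 0.40 × 16 = 6.4.

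- 4/16 = 25.0% fails. If all four misworded answers are yes, (4 + 4)/20 = 40.0% passes.
- 6/16 = 37.5% fails. If two of the four are yes, (6 + 2)/20 = 40.0% passes.
- 7/16 = 43.8% passes. If none of the four is yes, 7/20 = 35.0% fails.

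**How likely large *k* is**

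As an illustration, suppose the four are a random draw from the 50 enrolled. The expected *k* is then 4*n*/50, and P(*k* = 4) = C(*n*,4)/C(50,4), where C(50,4) = 230,300.

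| *n* | Expected *k* | P(*k* = 4) |
|---|---|---|
| 13 | 1.0 | 715/230,300 = 0.3% |
| 20 | 1.6 | 4,845/230,300 = 2.1% |
| 25 | 2.0 | 12,650/230,300 = 5.5% |

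The widest windows are therefore upper bounds. The middle rows are the more typical case.

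**The case against.** The strongest reply is that Measures already deals with the matter. It is the only place that mentions the error, it gives a reason and a rule, and the SAP sentence looks like generic text that was not updated. A careful analyst holding both would follow Measures. The logic there also points towards excluding the four, and the restriction may have been lost in the garbled sentence. The flip windows show what is possible, not what is likely: the widest need all four in the set and a particular pattern of answers. The set sizes are generous or loosely based, and weekly use is not identical to the per-protocol definition of at least four sessions in four weeks. No rule combines the five domains into one verdict, so a flip alters one result in one study. Reporting the percentage with and without the four would also end the silence.

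Much of this stands as a limit on size. The effect on the 40% verdict is not established and may be zero. It does not remove the defect. Reading one section as computing and the other as presenting does not reconcile them, because the computed Study 1 figure would rest mostly on answers that Measures declines to report. Exclusion within Study 2 can be inferred but is not written, and the literal set keeps the four.

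**Conclusion.** The concern holds. The two sections define different analysis sets for a primary feasibility domain, and following either one literally can count answers that the plan itself treats as unusable. For Study 1, the consequence is a descriptive percentage that should not be produced. For Study 2, between 0 and 4 misworded answers can enter the percentage. The verdict can change only when the valid result is near 40%: at an assumed *n* = 20, for a valid result of 7/19 if one is in the set, and for 4/16 to 7/16 (25% to 44%) if all four are. If none is, there is no effect. These sizes rest on assumed 1:1 allocation and assumed per-protocol counts of 13, 20 and 25. The textual conflict rests on no assumption. It should be fixed, though it does not threaten the trial as a whole.

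**What to change.** 1. In the SAP (Feasibility analyses), limit the payment tabulation to per-protocol Access participants in Study 2 who answered the corrected question, in place of those in each study.
2. In Measures (Willingness to pay), repair the duplicated phrase. State that answers to the misworded question are excluded from both numerator and denominator, and that the number excluded and the resulting denominator will be reported.
3. Attach the 40% criterion explicitly to that set, and state that it is not evaluated in Study 1.

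If the sponsor also wants the percentage with the four included, it can be shown as a labelled secondary figure, provided the set that decides the criterion is named.

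The cost is a few sentences and at most four Study 2 responses. Study 1 is then judged on four criteria instead of five, but that already follows from the restriction in Measures.

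### The uncontrolled within-session pain change is labelled the immediate effect of Rose and given a significance level, although it cannot separate a session effect from natural easing of pain

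*Combined protocol and SAP*

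**What the plan says.** **Collection.** Under Measures (secondary outcomes), the application asks for current pain on the 0-10 scale "just before and just after each listening session that included hypnotic suggestions for comfort". No rating of current pain is described at other times, after a neutral recording, or in people without access.

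**Arms.** The Overview states: "The Waitlist group will not have access to *Rose* for the first 4 weeks". Under Clinical effects analyses, Access sessions (8 weeks) and Waitlist sessions (the last 4 weeks) both enter the analysis.

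**Analysis.** The stated aim is "to estimate the immediate effects of the *Rose* sessions that target pain intensity". The plan first summarises the "average pre- to post-session changes in current pain intensity ratings for each participant individually". It then fits a linear mixed model to the change, separately in each study, with a participant random intercept and no other named term. This model is to give an effect size and the "significance levels of these changes".

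**Bias check.** The plan notes that people who find Rose particularly helpful "may choose to listen to more sessions than those who found" it less so, and will test whether benefit is related to the number of sessions. No other check is planned for this outcome.

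**Other clinical outcomes.** For the week-4 and week-8 outcomes, "no rigorous test of significance will be performed"; between-group effect sizes get 95% confidence intervals.

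**The concern.** Every pair of ratings brackets a Rose session, so there is no unexposed pair to compare it with. Randomisation does not help, because both arms supply only exposed sessions. No session schedule is given and listening frequency is itself an outcome, so participants appear to choose when to listen. If some of them tend to listen when pain is above its usual level, the second rating will on average be lower even if the session does nothing. A test of the mean change against zero would count that fall as benefit.

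The check on number of sessions asks whether frequent listeners respond differently. It does not ask at what pain level a session was begun.

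The stake is interpretation. The protocol uses the clinical estimates to judge whether the anticipated improvements are observed and to choose domains and measures for a full trial. The least controlled of these estimates is the one that would carry a p-value, and it would be named an effect of Rose.

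**Working it through.** **Figures in the documents.** The plan gives no power, effect size, SD or alpha for the immediate effect, so there is nothing of that kind to reproduce. The enrolment figure does reproduce: 50 × (1 − 0.20) = 40 completers per study. The expected use of about four sessions per 4 weeks of access gives about 8 for Access and 4 for Waitlist, an average of (8 + 4)/2 = 6 with equal arms and every session rated.

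**Assumed inputs.** The documents give none of these: excess of pre-session pain over the person's usual level, 1 to 2 points; correlation r between ratings 5 to 20 minutes apart, 0.7 to 0.9; between-person SD of the change, 0.7; within-person SD of the change, 1.2.

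**Step 1: fall expected with no session effect.** Fall = (1 − r) × excess.

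**Step 2: standard error.** SE = √(0.7²/40 + 1.2²/(40 × 6)) = √(0.01225 + 0.00600) = 0.135.

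**Step 3: z = fall/SE.**

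| Excess | r | Fall | z |
|---|---|---|---|
| 0 | any | 0 | 0 |
| 1 | 0.9 | 0.1 | 0.74 |
| 1 | 0.8 | 0.2 | 1.48 |
| 1 | 0.7 | 0.3 | 2.22 |
| 2 | 0.9 | 0.2 | 1.48 |
| 2 | 0.8 | 0.4 | 2.96 |
| 2 | 0.7 | 0.6 | 4.44 |

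Three of the six non-zero cells pass 1.96 and three do not.

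**Step 4: simulation of the planned model.** This used a different set of assumptions: no session effect, 40 participants, a mean of 8 or 4 sessions, momentary pain SD 1.5, between-person SD of change 0.3, two-sided 0.05, 600 runs per scenario. With sessions begun at usual pain (r = 0.90), 5% of runs were significant, as they should be. With sessions begun 1 SD (1.5 points) above usual, the share was 26% at r = 0.95, 64% at r = 0.90 and 96% at r = 0.80. The check on number of sessions was significant in 5 to 8% of runs throughout. In these runs session count was unrelated to the size of the fall, which is the case that the check is not built to find.

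**Step 5: can adjustment repair it?** An obvious idea is to add a covariate, pre-session pain minus the past-week average, and report the change where it is zero. Then adjusted change = raw change − b × (excess − reference error), where b is about −(1 − r) and reference error is how far the past-week average lies above current usual pain. With r = 0.8, b = −0.2:

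- excess 1, reference correct: −0.20 − (−0.2)(1) = 0.00; the bias is removed.
- excess 1, reference 1 point too high: −0.20 − (−0.2)(0) = −0.20; nothing is removed.
- excess 0, reference 1 point too high: 0 − (−0.2)(−1) = −0.20; a fall is created.

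Simulation with random error in the reference (SD 1) weakens the slope and gave about −0.05, −0.20 and −0.15 to −0.16 respectively. A reference that is too high is plausible: entry requires past-week average pain of at least 4, so baseline may lie above later usual pain, and any real improvement widens the gap.

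**The case against.** The strongest reply is that the easing is conjecture. Nothing in the documents says that sessions are begun at pain peaks. The feasibility standard of weekly use, modelled on how hypnosis is usually scheduled, fits routine listening at least as well. If sessions start at usual pain, or pain barely moves in 5 to 20 minutes, the bias is zero or small. This stands. A reader might infer that natural easing is in fact being counted as benefit; the documents support only that it cannot be excluded.

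Second, the framing is modest. The clinical outcomes are secondary, preliminary and unpowered, the section speaks of possible effects, and the descriptive part is about consistency of response within and between people. This limits the consequences, but it does not explain why a significance level is attached to this one uncontrolled quantity.

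Third, a reader might see a contradiction between the significance level here and the statement that "no rigorous test of significance will be performed". That statement concerns the week-4 and week-8 outcomes, so the two can coexist. What it shows is a more cautious stance for outcomes that do have a randomised comparison.

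Finally, one might object that a 95% interval excluding zero says the same as a p-value. Arithmetically it does, and it too reflects sampling error only. The change of label is therefore as necessary as dropping the p-value.

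**Conclusion.** The point holds as a limit on interpretation. As planned, the test of mean pre- to post-session change against zero cannot distinguish a Rose effect from natural easing, and the check on number of sessions does not address this. That follows from the design and needs no assumed number.

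The size cannot be derived from the documents. With an excess of 1 to 2 points and r of 0.7 to 0.9, a session with no effect would show a fall of 0.1 to 0.6 points, with z from about 0.7 to 4.4 under the assumed SDs; with no excess it is zero. Self-chosen timing is itself inferred from the absence of a schedule and from the plan's remark on choosing to listen more.

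The documents do not support the stronger reading that the observed change will be mainly artefact or that the trial's main conclusions are at risk. No feasibility criterion uses this change, and average pain intensity has its own randomised comparison at weeks 4 and 8.

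**What to change.** In Clinical effects analyses, replace the effect size and significance level for the session change with the mean change from the same mixed model and its 95% confidence interval, without a p-value. Describe the result, there and in reports, as an uncontrolled within-session change, not as the immediate effect of Rose. Add a sentence saying that natural easing cannot be excluded and that the check on number of sessions does not test for it.

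Optionally, describe pre-session pain relative to the past-week average from the most recent assessment: baseline, or week 4 for sessions after week 4. This would show whether sessions tend to be begun above usual pain. Any model adjusted for that difference should be marked exploratory, because a reference above current usual pain can leave or create a spurious fall.

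The cost is a change of wording and, for the option, a summary of ratings already collected. No new data are needed. The downside is a more modest claim for a secondary outcome.
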